7.8 SAFETY ENDPOINTS AND ANALYSIS

Summaries for safety parameters will be done for the Safety Set for Phase 1 and Phase 2a. Tables will be presented by dose level for Phase 1 and by Expansion Arm for Phase 2a.

7.8.1 EXPOSURE TO STUDY TREATMENT

Total exposure (planned and actual) to the AFM24 in mg will be summarized by visit and overall. Delays, Interruptions, Dose Adjustments and Deviations and reasons for those will be summarized as well. Listings of AFM24 exposure data (doses and all dose adjustments/deviations) will be created.

For Phase 2, the overall number of cycles, Duration of Exposure, Dose Intensity and Relative Dose Intensity will be summarized. Duration of Exposure in weeks will be defined as (date of the last AFM24 injection – date of the first AFM24 injection +7)/7. The above rule applies for weekly doses of AFM24, for the biweekly schedule the rule will be (date of the last AFM24 injection – date of the first AFM24 injection +14)/7. Dose Intensity will be defined as the total amount of AFM24 received by the subject in mg divided by the Duration of exposure. Relative Dose

CONFIDENTIAL

Page 19 of 22

Statistical Analysis Plan template version 1.0 dated 27-MAR-2019

Intensity will be calculated as the total dose of AFM24 received divided by the planned dose per cycle times the number of initiated cycles.

The Exposure data will be summarized both for DDS and the Safety Set in Phase 1.

7.8.2 ADVERSE EVENTS

AEs will be summarized with patient counts, percentages and event counts by MedDRA System Organ Classes (SOCs) and Preferred Terms (PTs). Following categories of AEs will be summarized: AEs, related AEs, SAEs and related SAEs, AEs with NCI CTCAE Grades ≥ 3 , AEs leading to premature discontinuation and interruptions or discontinuation of study drug and TEAEs on day of dosing (up to 24h after the dose) and on the first day after the dose. An event will be considered study drug related if it has 'possible', 'probable' or 'definitely' in relationship to study drug CRF field. TEAEs presented by SOC and PT will also be summarized by severity grades. For all TEAEs' summaries a number of patients with the event will be presented together with the total number of TEAEs.

A worst-case approach will be followed in the event of missing severity or causality data. If the severity is missing, severity grade "4" will be imputed. If causality data is missing, 'Related to study medication' will be imputed.

Listings of AE data (separate for each AE category listed above) will be created.

Summaries of all deaths reported and deaths within 28 days after the last dose of study drug along with causes of death will be created. Listing of the death data will be created.

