5.2 Study Drug Administration

All doses of AFM24 will be administered as an i.v. infusion. During the dose escalation phase (Phase 1), subjects will receive AFM24 as a weekly infusion. As mentioned in Section 3.1, additional dosing regimen (i.e., q2w) may be explored in the dose expansion phase (Phase 2a) **only**.

For dose escalation phase (Phase 1) and dose expansion phase (Phase 2a)

- Weekly dosing regimen (q1w): i.e., on Day 1, Day 8, Day 15, and Day 22 of a 28-day cycle (see APPENDIX A [Section 14.1]).

For dose expansion phase (Phase 2a) only

In addition to the weekly dosing regimen mentioned above, the following dosing regimen may be used:

- Every-2-weeks dosing regimen (q2w): i.e., on Day 1 and Day 15 of a 28-day cycle (see APPENDIX B [Section 14.2]). If the drug is given on a q2w schedule, the daily dose will not be higher than the highest daily dose that was tested in Phase 1 part of the study and was considered safe.

The baseline infusion time should not take less than approximately 4 hours for at least the first 2 AFM24 infusions (**Note:** infusion time is approximately 4 hours, any infusion time \geq 3 hour 50 minutes will not be a deviation). It should also be noted that as the dose escalation continues into the higher dosing cohorts, the baseline infusion time may increase to >4 hours and as long as over 2 days (ie, split day dosing) based on a given subject's tolerability as detailed in the Pharmacy Manual for each cohort. For infusion times that span over 2 days (i.e., split day dosing), timepoints for different assessment may be affected and the Schedule of Assessment (SoA) tables should be referenced for details (See Section 14.1 and Section 14.2 for SoA tables

for weekly and q2w dosing schedules, respectively). If the first 2 consecutive AFM24 infusions are well tolerated (defined as no IRR/cytokine release syndrome (CRS) Grade >1), then the infusion time may be decreased to <4 hours to a minimum of 1 hour starting with the third subsequent infusion (ie, C1D15 for weekly dosing regimen and C2D1 for q2w dosing regimen) at the discretion of the Investigator along with a potential reduction of post infusion- observation period (with regular checks of vital signs, please refer to [Table 5](#) for detailed description) from 4 hours to a minimum of 2 hours and a taper of corticosteroid premedication. Investigators should only make 1 modification per infusion at 1 time.

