5.3 Premedication Regimen and Post-Dose Observation

Subjects are required to receive premedication with the following medications approximately 1 hour before each dose of AFM24:

- i.v dexamethasone 20 mg (or equivalent long-lasting steroid dose)
- i.v. H1 antagonist (e.g., diphenhydramine 50 mg or similar medication as used per local institutional practice) with or without an H2 antagonist (e.g., famotidine or similar medication as used per local institutional practice), and
- acetaminophen dosage as per local institutional practice (e.g., 650 mg to 1000 mg or equivalent).

Note: For infusion times that span over 2 days (i.e., split day dosing), subjects must receive premedication on Day 1 and as well on Day 2. This includes the H1 antagonist (with or without an H2 antagonist), acetaminophen, and dexamethasone. For Day 2, dexamethasone dose can be reduced to a minimum of 8 mg, according to local standards at the discretion of the Investigator/treating physician.

Subjects may also be administered prophylactic antiemetic medications as indicated. Additional oral premedication will be allowed on the day before each dose of AFM24 at the discretion of the Investigator, in particular for those subjects who may experience persistent IRR.

If the first 2 subsequent infusions are well tolerated (defined as no Grade >1 IRR/CRS), then the medication(s) within the premedication regimen can be tapered/decreased.

Clinicians should be prepared for an IRR or CRS to occur during or shortly after each AFM24 drug administration, with frequent monitoring of vital signs and medical equipment and supplies readily available and standing orders in place for immediate intervention. Please see APPENDIX F (Section [14.6](#)) for details regarding treatment management for symptoms of IRR/CRS due to study drug.

After the first 2 subsequent doses of AFM24 subjects must be observed for at least 4 hours after the end of infusion (EOI), with regular checks of vital signs as described in Section [7.2.4](#).

In case of a split day dosing (over 2 days) subjects must be observed for at least 4 hours after the end of AFM24 infusion on each day. In this scenario, the split day dosing AFM24 infusion is considered 1 dose. If no signs or symptoms of CRS or an IRR (no Grade >1) are observed during or after the first 2 subsequent doses of AFM24 then the observation period following each AFM24 dose may be reduced from 4 hours to at least 2 hours after the end of infusion.

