8.1.3 Evaluating Adverse Events

During pre-screening, only AEs which are related to study procedures (e.g., a biopsy) should be collected. The AEs must be recorded and described on the appropriate AE page of the eCRF

Following the subject's written Main consent to participate in the study and up to the 30-day Safety Follow-up Visit, all AEs should be collected.

Adverse events that occur following signing of the Main ICF but prior to the first dose of study drug shall be recorded on the Medical History page of the eCRF.

Adverse events occurring after the subject signs the Main ICF and at/after the first dose of study drug and up to the 30-day Safety Follow-up Visit must be recorded and described on the appropriate AE page of the eCRF. (**Note:** any SAEs that are related to study procedures and occur during pre-screening and any SAEs that occur following signing the Main ICF and prior to the first dose of study drug will still be reported using the SAE form). Where known, the diagnosis of the underlying illness or disorder shall be recorded, rather than listing individual symptoms.

Please refer to [Table 6](#), which describes the timelines of AE/SAE reporting and documentation in the eCRF.

The following information shall be captured for all AEs: date of onset and resolution, seriousness and seriousness criteria, severity of the event, causality assessment, treatment required for the AE, action taken with study drug, and information regarding resolution/outcome.

Table 6: Reporting of Adverse Events

	... between Pre-Screening ICF and Main ICF	... between Main ICF and first infusion	... at/after first infusion
AE unrelated to Study Procedure occurs ...	no documentation needed	document in medical history	document as AE
AE related to Study Procedure occurs ...	document as AE	document in medical history	document as AE
SAE unrelated to Study Procedure occurs ...	no documentation needed	document as SAE	document as SAE
SAE related to Study Procedure occurs ...	document as SAE	document as SAE	document as SAE

Abbreviations: AE = adverse event; ICF = informed consent form; SAE = serious adverse event

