7.3 HANDLING OF MISSING DATA

The following approach will be used to impute missing start date of Adverse Events and Concomitant Medications:

- If only day is missing and the month and the year match the date of the first study drug injection, then impute the first date of the study drug injection
- If only day is missing and the month and the year do not match the date of the first study drug injection, then impute the first day of the month
- If the day and the month are missing and the year matches the date of the first study drug injection, then impute the first date of the study drug injection
- If the day and the month are missing and the year does not match the date of the first study drug injection, then impute 01 January of the year

Details of imputation of missing severity and causality for Adverse Events are given in Section 7.8.2. No other imputation for the missing data will be done.

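### Adverse events with an imputed start date enter the SAP's day-of-dosing table as if they were acute, and the two acute windows are not defined well enough to program

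*SAP*

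**What the plan says.** Four places bear on this.

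- **SAP 7.8.2** lists among its adverse event categories "TEAEs on day of dosing (up to 24h after the dose) and on the first day after the dose". It does not say whether time runs from the start or the end of infusion, whether a day means a date or 24 hours, or whether the two windows exclude each other. For each such summary, "For all TEAEs' summaries a number of patients with the event will be presented together with the total number of TEAEs".
- **SAP 7.3** handles partial start dates. If the day is missing and the month and year match the first dose, or if only the year is known and it matches, "then impute the first date of the study drug injection". If they do not match, the event goes to the first of the month or to 1 January. SAP 7.8.2 neither excludes nor flags events dated this way.
- **Protocol 8.1.3** names the data to collect: "The following information shall be captured for all AEs: date of onset and resolution, seriousness and seriousness criteria, severity of the event". Clock time of onset is not in the list.
- **Protocol 5.2** allows one infusion to run over two days, and Protocol 5.3 adds, for the observation rule, that "the split day dosing AFM24 infusion is considered 1 dose". The SAP gives no window rule for this case.

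The dosing-day and next-day windows appear only in the SAP. The adverse event analysis in Protocol 9.3.6.1 does not have them.

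**The concern.** Placing a partial date on the first-dose date is a usual, cautious choice when the question is whether an event was treatment-emergent. It is not evidence that the event began on the day of infusion. Once the imputed date feeds a table whose only purpose is to show what happened on dosing days, the caution becomes a statement about timing that the data do not support. An event known only by its year could have begun months later.

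Characterising both acute and chronic toxicity is a secondary objective in both phases, and these two tables are the only adverse event summaries in the plan that separate events by time from dosing. Infusion-related reactions were the most frequent treatment-emergent event in Protocol 1.6 (69%), and Protocol 8.3.1 says most occur with the first infusion. The imputed events therefore land on the infusion where the real acute signal is expected, in Phase 1 tables split by dose level with few subjects in each.

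The loose window wording adds a second problem: two programmers could produce different tables from the same data.

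**Working it through.** The plan gives no figure to reproduce. The check has four parts.

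**1. Effect of one imputed event.** The patient count in a preferred-term row rises by at most 1/n. Cohort sizes come from Protocol 3.4 (at least 2 in the first two cohorts, at least 3 later, expansion up to 6).

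- n = 2: 1/2 = 50 points
- n = 3: 1/3 = 33 points
- n = 6: 1/6 = 17 points

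These are maxima. The row does not move if the subject already has that preferred term on a dosing day. The event count rises by one in any case.

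**2. How often the imputed date would be right.** Assume a 30-day month, first dose on day d, and onset equally likely on each day from d to 30. The chance that onset was truly on the first-dose date is 1/(30 − d + 1). Because the table covers dosing days in general, I also count weekly doses falling on days d, d+7, d+14 and so on within the month.

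| First dose on day | Chance of first-dose date | Chance of any dosing date |
|---|---|---|
| 1 | 1/30 = 3.3% | 5/30 = 16.7% |
| 15 | 1/16 = 6.3% | 3/16 = 18.8% |
| 22 | 1/9 = 11.1% | 2/9 = 22.2% |
| 29 | 1/2 = 50% | 1/2 = 50% |

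The rule places the event on the first-dose date with certainty. The uniform assumption is for illustration; infusion reactions cluster at the first dose, so it does not describe them.

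**3. Whether the windows overlap.** Assume infusion starts at 08:00 to 12:00. Let window 1 be the 24 hours from an anchor time and window 2 the next calendar day. The shared time equals the anchor's clock hour.

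- Anchor at start of infusion: 8 to 12 h, or 8/24 = 33% to 12/24 = 50% of the next day.
- Anchor at end of a 4-hour infusion: 8 + 4 = 12 h to 12 + 4 = 16 h, or 50% to 67%.
- Both windows by date, or window 2 read as 24 to 48 h: 0 h.

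Overlap therefore depends on the reading, and the SAP does not choose one. The percentages are shares of clock time, not of events.

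**4. Split dose.** Day 2 of a two-day infusion is a day on which drug is given, and also the day after the dose began. If the one-dose statement in Protocol 5.3 carries over, Day 2 is a dosing day only. If each day's portion is taken separately, it is also the first day after the Day 1 portion. The SAP does not settle which applies.

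**The case against.** The strongest reply is that this is loose wording in a descriptive table. Much of that stands.

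- A reader might infer that acute events are double-counted. The plan does not support this. The categories in SAP 7.8.2 are separate and deliberately not exclusive (a serious event also appears under all events), and nothing adds the two windows together. The most that can happen is that one event shows in both tables and blurs the contrast between them.
- A reader might also take the overlap, or the presence of all of Day 2 in both windows, as fact. Each holds under one reading and disappears under another.
- Nor do the documents show that acute toxicity is overstated overall. A next-day event within 24 hours of the dose is still acute, and the number of partial dates is not given. Infusion reactions are events of special interest, reportable within 24 hours, and Protocol 8.3.1 asks for detail on symptom timing, so a missing onset day is unlikely for them.
- The case report form and table shells are not available here. Onset time may be collected although Protocol 8.1.3 does not list it.
- Imputing towards the first dose matches the worst-case approach that SAP 7.8.2 takes for missing severity and causality.

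The last point does not rescue the day-of-dosing table. A worst case for severity or causality is a bound on risk. Assigning a date in a timing table is a claim about when the event happened, and SAP 7.3 and 7.8.2, followed exactly, make that claim without support.

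**Conclusion.** The point holds in a limited form. The firm part is the imputation: the two SAP rules together put events of unknown onset day into the day-of-dosing table, with no exclusion or flag. The size is at most 33 points per event in a preferred-term row for a 3-subject cohort and 17 points for a 6-subject cohort. The total effect cannot be estimated, because it depends on how many start dates are partial. The other three gaps (mixed 24-hour and calendar-day wording, a 24-hour limit not derivable from the onset date the protocol names, and no rule for Day 2 of a split dose) would on their own call only for clarification.

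No overall adverse event total, DLT count, BLRM update or Simon decision depends on these tables. It is worth correcting because these are the only summaries that address acute timing and the correction is cheap.

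**What to change.** In SAP 7.8.2, define two exclusive windows on onset date, separately for each dose:

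1. the infusion date, or both dates of a split dose;
2. the next calendar day after the last infusion date of that dose.

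Drop the 24-hour limit unless onset time is collected. Leave events whose onset day was imputed under SAP 7.3 out of both window tables, report their number in a footnote, and keep them in all overall adverse event tables and listings. The imputation rule can stay as it is for flagging treatment emergence.

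The cost is a few lines of SAP text and one derived variable. No new data are needed. The small downside is that next-day events within 24 hours of the dose move to the second table, so the two tables should be read together when late or overnight reactions are of interest.

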7.8.3 LABORATORY DATA

Safety laboratory results (Serum Chemistry, Hematology, and Coagulation) will be graded by NCI CTCAE v5.0 if no grading exists values will be classified into low/normal/high based on laboratory normal ranges. As only the local laboratory data are collected, no quantitative summaries of the laboratory data will be created. Urinalysis results will be summarized categorically.

For laboratory results reported with a "<" sign, half of the value that follows will be used for the analysis. Results reported after ">" sign will be analyzed as is.

Shift tables classified by reference range indicator (Low, Normal, and High) and also by CTCAE toxicity grades (worst toxicity grade in a period from the first dose until final visit, not including Follow-Up period) from baseline will be presented separately by laboratory test, where applicable.

All laboratory values will be listed. A separate listing for abnormal lab values (Grade 3 and higher, and low/high values) will be presented.

7.8.4 VITAL SIGNS AND OTHER SAFETY PARAMETERS

Vital signs will be summarized by descriptive statistics at each visit including change from baseline will be presented and a listing will be provided.

Local-read ECG data will be listed overall and a separate listing for any clinically significant finding in ECG values will be provided. The frequency and percentage of patients with clinically

significant ECGs and newly occurring qualitative ECG abnormalities will be tabulated as well. The summaries will only be done for Phase 1, Phase 2 ECG data will only be listed.

Physical Examination data will be summarized by visit. Listing of the PE data will be created.

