3.4.2 Definition of Dose-Limiting Toxicity (DLT)

Dose-limiting toxicity is defined as an AE or abnormal laboratory value assessed as unrelated to underlying disease, disease progression, inter-current illness, or concomitant medications, that occurs ≤ 28 days following the first dose of AFM24 (Cycle 1) and that meets any of the following criteria shown in Table 3. Clinically relevant toxicities will be evaluated according to the National Cancer Institute (NCI)/National Institutes of Health CTCAE v5.0. Subjects who experience a DLT during Cycle 1 must permanently discontinue AFM24.

Subjects must receive $\geq 80\%$ of their assigned AFM24 dose in Cycle 1 and complete the 28-day DLT observation period or have had a DLT within the first cycle of treatment to be considered evaluable for DLT.

For dose-escalation decisions, only DLTs occurring during Cycle 1 of treatment will be considered in the 2-parameter BLRM.

Table 3: Definition of Dose Limiting Toxicity

Toxicity	Any of the following criteria
Hematological ^a	\geq CTCAE Grade 4 neutropenia (ANC $<0.5 \times 10^9/L$) lasting for longer than 4 consecutive days
	Febrile neutropenia (ANC $<1.0 \times 10^9/L$ of any duration accompanied by fever $\geq 38.5^\circ C$ or systemic infection)
	CTCAE Grade 3 thrombocytopenia (platelets 25 to $<50 \times 10^9/L$) associated with bleeding
	CTCAE Grade 4 thrombocytopenia (platelets $<25 \times 10^9/L$)
	\geq CTCAE Grade 4 anemia that is considered to be treatment related
Non-hematological	
Any \geqCTCAE Grade 3 AE including, but not limited to:
 
• CTCAE Grade 3 infusion-related reaction/cytokine release syndrome not responsive to symptomatic treatment within 6 hours (ie, no improvement to Grade 2 or better within 6 hours with optimal medical management)• CTCAE Grade 4 infusion-related reaction/cytokine release syndrome• QTcF prolongation (>500 msec)

Toxicity	Any of the following criteria

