7.2.6 Clinical Chemistry, Hematology, Urinalysis, Coagulation

Blood and urine samples for determination of clinical chemistry, hematology, urinalysis, and coagulation parameters will be taken as described in the SoA tables (APPENDIX A [Section 14.1] for weekly dosing schedule and APPENDIX B [Section 14.2] for q2w dosing schedule). Subjects must demonstrate adequate organ function when assessed within 14 and 7 days before first AFM24 infusion to remain eligible as outlined in the inclusion criteria (Section 4.1). Clinical chemistry, hematology, urinalysis, and coagulation samples must be

taken within 24 hours of AFM24 infusion start on days when AFM24 is administered. In case a subject receives AFM24 as a split dose then the time period ‘within 24 hours’ refers to the first day of infusion onset (ie, if infusion is given as split dose on both Day 1 and Day 2 [in weekly dosing regimen], then these samples need to be collected within 24 hours of AFM24 infusion start on Day 1).

Hepatitis B, hepatitis C, and HIV serology testing will be performed at Screening.

The laboratory variables to be measured are described in APPENDIX D [Section 14.4].

Copies of laboratory accreditation certificates and reference ranges will be obtained from each study site prior to analysis of their first subject sample and maintained over the course of the study.

If a clinically significant clinical chemistry, hematology, urinalysis, or coagulation finding is identified during the study, the Investigator will assess whether this finding is also considered an AE.

7.2.7 **Electrocardiogram**

A resting 12-lead ECG will be performed at timepoints specified in the SoA tables (APPENDIX A [Section 14.1] for weekly dosing schedule and APPENDIX B [Section 14.2] for q2w dosing schedule). **For Phase 1 only**, triplicate

ECGs should be taken at least 5 minutes apart before infusion and within approximately 15 minutes after the end of infusion (note plus only). **For Phase 2a**, ECGs will be performed in triplicate at least 5 minutes apart at the Screening visit only; all subsequent ECGs will be performed as single ECGs.

For those occasions when both an ECG and peripheral blood sample (PK and PD [cytokines]) collection are required at the EOI of AFM24 (ie, Cycle 1 Day 1 and Day 22), the blood draw must be completed first, as close to the EOI as possible, followed by the ECG. Both procedures should be completed within approximately 15 minutes after the EOI (note plus only).

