9.3.6.4 Electrocardiogram

Local-read ECG data will be listed overall and a separate listing for any clinically significant finding in ECG values will be provided. The frequency and percentage of subjects with notable ECGs and newly occurring qualitative ECG abnormalities will be tabulated by cohort.

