- j. For the dose escalation phase (Phase 1), ECG is required on Cycle 1 Day 1 and Day 22, before infusion and within 15 minutes after the EOI (+15 minutes, note plus only). When both an ECG and peripheral blood sample collection (PK and PD [cytokines]) are required at the EOI of AFM24 (ie, Cycle 1 Day 1 and Day 22), the blood draw must be completed first as close to the EOI as possible, followed by the ECG. Both procedures should be completed within 15 minutes after the EOI (+15 minutes, note plus only). For Phase 2a, ECG is not required on Cycle 1 Day 1 and Day 22. ECG assessments are to be performed with the subject in the supine position. For the dose escalation phase (Phase 1) only, all ECGs should be performed in triplicate at least 5 minutes apart. For the dose expansion phase (Phase 2a), ECGs will be performed in triplicate at least 5 minutes apart at the Screening visit only. All subsequent ECGs will be performed as single ECGs.
- k. Hematology (including coagulation) parameters include red cell count, mean corpuscular volume, hemoglobin, hematocrit, reticulocyte count, platelet count, white blood cells, leukocyte differential count (% and/or absolute), international normalized ratio or prothrombin time, and activated partial thromboplastin time (See [APPENDIX D](#), Section [14.4](#)).
- l. Phase 1 without split day dosing: Additional blood sample for hematology on Cycle 1 Day 1 and Day 22 should be collected 1 hour after EOI (± 15 minutes).
Phase 2a without split day dosing: Additional blood samples for hematology on Cycle 1 Day 1 and Day 22 should be collected after EOI (+15 minutes, note plus only) at sites that can perform the PBMC isolation according to the lab manual/Sponsor requirements.
- m. Phase 1 and Phase 2a with split day dosing: Blood sample for hematology on Cycle 1 Day 2 and Day 23 should be collected after EOI (+15 minutes) at sites that can perform the PBMC isolation according to the lab manual/Sponsor requirements.
- n. Clinical chemistry parameters include calcium, total protein, albumin, total bilirubin, alanine transaminase, aspartate transaminase, lactate dehydrogenase, alkaline phosphatase, glucose (random), sodium, potassium, bicarbonate, chloride, magnesium, urea (blood urea nitrogen), creatinine, phosphate, uric acid, amylase, lipase, and C-reactive protein (See [APPENDIX D](#), Section [14.4](#)).

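### SAP 7.8.4 plans no numeric QTcF summary of the Phase 1 triplicate ECGs, so a modest QTcF change could not be estimated from the planned tables

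*SAP*

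**What the plan says.** **Collection.** Protocol 7.2.7 requires that Phase 1 triplicate "ECGs should be taken at least 5 minutes apart before infusion and within approximately 15 minutes after the end of infusion". Table 11, footnote j (Appendix A) fixes the days: "ECG is required on Cycle 1 Day 1 and Day 22, before infusion and within 15 minutes after the EOI". The same footnote says "For the dose escalation phase (Phase 1) only, all ECGs should be performed in triplicate at least 5 minutes apart". Where an end-of-infusion PK and cytokine sample is also due, "the blood draw must be completed first, as close to the EOI as possible, followed by the ECG". Table 12 schedules PK at end of infusion on both days.

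**Numeric use of QTcF.** Exclusion criterion 7 rejects a Fridericia-corrected QT above 470 msec, taken as the mean of three ECGs. Protocol Table 3 makes "QTcF prolongation (>500 msec)" a DLT.

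**Analysis.** Protocol 9.3.6.4 plans listings, and then: "The frequency and percentage of subjects with notable ECGs and newly occurring qualitative ECG abnormalities will be tabulated by cohort". SAP 7.8.4 plans the listings ("Local-read ECG data will be listed overall and a separate listing for any clinically significant finding in ECG values will be provided") and counts of patients with clinically "significant ECGs and newly occurring qualitative ECG abnormalities will be tabulated as well". It restricts those counts to Phase 1 and only lists the Phase 2 ECGs. Neither document defines *notable* or *clinically significant*. QTcF appears in the SAP abbreviation list and in none of its analyses. Vital signs, in the same SAP section, do get descriptive statistics and change from baseline.

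**The concern.** QTcF is a continuous measurement, and the Phase 1 schedule is laid out to measure it well: three recordings per timepoint, a same-day value before infusion, and a second set beside the end-of-infusion PK sample. The planned tables turn this into a yes/no judgement by the local reader.

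The entry limit is 470 msec and the only numeric on-treatment rule is 500 msec. A mean increase of 10 or 20 msec would leave most subjects well below that rule, and nothing in the two tabulated categories is tied to a size of change. The report would then have no estimate of the QTcF change and no interval around it, although safety and tolerability are part of the Phase 1 primary objective.

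The wording of the two documents also drifts. *Notable* becomes *clinically significant*, and tabulation by cohort becomes Phase 1 only. SAP section 9 reports no deviation from the protocol beyond a change it does not identify.

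**Working it through.** The plan states no QT effect size, margin, variability or power, so there is no figure to reproduce. The check has a document part and an illustrative part.

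**1. What the planned output can show**

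| Item | Collected or defined | Planned in SAP 7.8.4 |
|---|---|---|
| Three ECGs per timepoint | Yes (Protocol 7.2.7, Table 11) | No averaging rule |
| Same-day pre-infusion value | Yes, C1D1 and C1D22 | No change from baseline |
| QTcF in msec | 470 (entry), 500 (DLT) | Listed only, no categories |
| End-of-infusion PK beside the ECG | Yes | No exposure-QTcF analysis |

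The general baseline rule in SAP 7.2 takes the last non-missing value before first dose. Applied to triplicates without an averaging rule, that could select one of the three recordings.

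**2. What the 500 msec rule alone would pick up (illustration)**

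Assumptions, none from the documents: baseline QTcF normal with mean 420 and SD 20 msec, cut at the 470 msec entry limit; individual change normal with mean Δ and SD s of 10 to 15 msec. The number of subjects, n = 25 to 41, is the Phase 1 range in Protocol 3.4 (SAP 3.2 says 25 to 35).

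- p = average over baseline values b of P(Z > (500 − b − Δ)/s)
- P(at least one subject above 500) = 1 − (1 − p)^n

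Example: Δ = 10, s = 15 gives p = 0.00133. Then 1 − 0.99867^25 = 3.3% and 1 − 0.99867^41 = 5.3%.

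| Mean shift Δ | P(at least one subject > 500), s = 10 to 15, n = 25 to 41 |
|---|---|
| 10 msec | 0.3% to 5.3% |
| 20 msec | 3.4% to 21% |
| 30 msec | 19% to 54% |
| 60 msec | 99% or more |

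With a lower and tighter baseline (mean 410, SD 15), the 20 msec row falls to 0.1% to 1.9% and the 60 msec row to 71% to 97%. So this rule would usually miss a modest shift and would usually catch a gross one.

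**3. What a change-from-baseline summary would give (illustration)**

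Half-width of a two-sided 90% CI for the mean change = t(0.95, n − 1) × SD/√n. Example: n = 25, SD 15 gives 1.711 × 15/5 = 5.1 msec.

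| n | SD 10 | SD 15 | SD 20 |
|---|---|---|---|
| 3 (minimum cohort from Cohort 3 on) | 16.9 | 25.3 | 33.7 |
| 6 (maximum expanded cohort) | 8.2 | 12.3 | 16.5 |
| 25 (Phase 1 low) | 3.4 | 5.1 | 6.8 |
| 41 (Phase 1 high) | 2.6 | 3.9 | 5.3 |

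These n are planned enrolment. Subjects with both triplicate sets may be fewer. Parts 2 and 3 answer different questions and should not be read as rival powers: the planned table counts ECGs judged significant or newly abnormal, not values above 500 msec, and its chance of staying empty cannot be computed from the documents.

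**The case against.** The strongest reply is that important QT effects are already covered. QTcF above 500 msec in Cycle 1 is a DLT and enters the dose-escalation model. Protocol 7.2.7 has clinically significant ECG changes from baseline recorded as AEs, which are tabulated. The SRC reviews all available safety data for each cohort, and every local-read ECG is listed. This stands. A reader might infer that the plan cannot detect any QT effect, or that its table will be empty whatever the drug does. The documents do not support either reading.

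A second reply is that the added summary would prove little. By-dose estimates rest on 3 to 6 subjects. At the stated data cutoff (Protocol 1.6) the pooled group spanned 14 to 480 mg, a range of 480/14 ≈ 34-fold, so a pooled mean describes no single dose. There is no control. Dexamethasone and an H1 antagonist are given about one hour before each dose, and infusion-related reactions were reported at 69%. All of this stands. A reader might infer that the new tables could exclude a QT effect or attribute one to AFM24, and they could not. They would describe the change and its uncertainty.

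Third, SAP 7.8.3 declines quantitative laboratory summaries because only local data are collected, so a categorical treatment of local ECGs is consistent. This carries less weight: the comparison here is within subject, and Protocol 7.2.7 asks for an identical machine for each subject.

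Fourth, the protocol sets no QT objective, reports no AFM24-related ECG effect in monkeys, and promises in its synopsis to examine dose, safety and PK relationships. The PK analysis plan and table shells were not available, so QTcF work there cannot be ruled out. No supplied text names any.

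Finally, the listing-only handling of Phase 2a might look like a serious loss. It is not: scheduled ECGs there are at screening and end of treatment only, and the protocol's phrase about cohorts does not clearly mean expansion cohorts.

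**Conclusion.** The point holds in a limited form. Phase 1 collects triplicate, PK-timed ECGs, and the SAP specifies no numeric QTcF analysis of them. Gross prolongation would probably come to light through the DLT rule or AE reporting. A modest mean change could not be estimated from the planned tables.

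The gap itself follows from the documents and needs no assumption. Its size does: with an assumed SD of change of 10 to 20 msec, a pooled 90% CI would have a half-width of 2.6 to 6.8 msec, against 8.2 to 33.7 msec in a cohort of 3 to 6. The pooled figure is therefore reasonably precise but mixes doses, and the by-dose figures are rough. Any power or detection figure is illustrative only, because the documents give no QTcF variability.

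The two undefined terms and the unrecorded Phase 2a restriction are smaller matters of consistency.

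**What to change.** In SAP 7.8.4, with matching text in Protocol 9.3.6.4:

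1. Average the triplicate QTcF at each timepoint, and say that this mean replaces the last-value rule of SAP 7.2 for ECG baselines.
2. Summarise QTcF at end of infusion on C1D1 and C1D22, and its change from the same-day pre-infusion value and from the C1D1 pre-dose value. Give the mean and 90% CI by dose level and pooled.
3. Tabulate numeric QTcF categories, including the protocol's own 470 and 500 msec, and increases above 30 and above 60 msec. Use these to define *notable*, and use one term in both documents.
4. Present the results as descriptive, stating the limits: small cohorts, a pooled mean across doses, local reads, no control, and premedication before each dose.
5. Record the listing-only handling of Phase 2a ECGs as a deviation in SAP section 9, or reconcile it with Protocol 9.3.6.4.

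The cost is SAP and protocol wording and a few tables from data already collected. No ECG, visit or reader is added. Specifying the summary before the data are analysed is better than adding it later from the listings.
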